3.7 Risks / Benefits

Despite strong reasons for a benefit of rhC1INH in the setting of hyperinflammation, it is unclear if participants in the current study will receive any immediate benefit from treatment with rhC1INH. However, the knowledge gained from this study may help to better understand the pathophysiology of ALI and hyperinflammation in SARS-CoV-2 and related CoV infections. In addition, this trial may serve as pilot study for future rhC1INH studies in patients with severe infections characterized by hyperinflammation and subsequent tissue damage.

Previous experimental models have not suggested a detrimental effect of complement inhibition on viral replication, and C1-INH treatment has not been associated with an increased risk for secondary bacterial or viral infections in humans.

RhC1INH is approved for the treatment of acute angioedema attacks in adult and adolescent patients with HAE in the EEA countries and the United States and for adults in South Korea and Israel. Up to October 2019, 268 unique patients have been exposed to rhC1INH in the rhC1INH clinical development program and 3717 patients worldwide have been commercially prescribed rhC1INH without any change to the risk-benefit profile.

To date, the only known relevant clinical risk associated with rhC1INH is the possibility of an allergic reaction to Host-Related Impurities (rabbit). Patients with medical history of allergy to rabbits or rabbit-derived products including rhC1INH or suspicion of such an allergy, are excluded from participation.

To minimize the risk for allergic reactions to rhC1INH, treated patients will be monitored for clinical symptoms of hypersensitivity during and after dosing. All treatments will be administered in a hospital and all patients will stay under close observation until discharge from the hospital.

RhC1INH was demonstrated to be a safe option for reducing the risk of contrast-induced renal damage in high-risk patients⁴². In addition, rhC1INH was safely administered to five patients suffering from stage II COVID-19 infection.

Expected Adverse Events During the Study

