As per last the Investigator's Brochure, expected adverse reactions are described as follows: The clinical development program supporting safety of rhC1INH is based on a total number of 268 unique patients (up to Oct 2019). Those 268 patients received a combined total of almost 1600 administrations of rhC1INH. The treatment emergent adverse events (TEAEs) that occurred with onset within 7 days of treatment with rhC1INH that were most frequently reported (observed in $\geq 3\%$ of patients treated with rhC1INH) were headache (11%), nausea, and

diarrhea (3% each). There was no evidence of an increase in the percentages of patients with TEAEs or related TEAEs, or in the seriousness or severity of TEAEs, with increases in rhC1INH dose, treatment of a larger number of attacks, and/or treatment of a single attack with an additional dose.

As described in the US prescribing information for rhC1INH, AEs of headache, sneezing, angioedema, erythema marginatum, skin burning sensation, back pain, C-reactive protein increased, fibrin D-dimer increased, vertigo, lipoma, nausea, and diarrhea occurred in $\geq 2\%$ of rhC1INH -treated patients. Note that AEs are listed in the US prescribing information regardless a causal relationship with rhC1INH. The frequency of adverse reactions listed above is defined using the following convention:

- Very common ($\geq 1/10$),
- Common ($\geq 1/100$ to $< 1/10$),
- Uncommon ($\geq 1/1,000$ to $< 1/100$),
- Rare ($\geq 1/10,000$ to $< 1/1,000$),
- Very rare ($< 1/10,000$),

Specific antidotes against rhC1INH do not exist. In the unlikely event of an allergic reaction, standard treatment regimens indicated by the clinical situation (e.g. epinephrine, antihistamines, corticosteroids, etc.) will be administered.

The level of risk may evolve over time, during the study: consequently, a Data Safety Monitoring Board (DSMB) will monitor the safety of all patients, as well as the continuing validity and scientific merit of the study.

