10.1.4 Ongoing Safety Monitoring and Stopping Rules

Adverse events and abnormal lab values will be graded using the Common Terminology Criteria for Adverse Events (CTCAE) Version 5.0. A subject who experiences a treatment-emergent anaphylactic/anaphylactoid reaction or thrombotic/thrombo-embolic event will not be permitted to receive further treatment with study drug until the review of the case, discussion with the treating Investigator and Pharming, and further evaluation as required is completed.

Further enrollment into the study, and further rhC1INH administration in all subjects, will be temporarily halted pending a review of the data if either of the following occur:

- If one or more subjects experience a Grade 4 or Grade 5 adverse event possibly related to study drug administration, as assessed by the Investigator or Pharming, or
- If two or more subjects experience a Grade 3 adverse event possibly related to study drug administration.

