4 TRIAL OBJECTIVES

Overall Objective

The purpose of this study is to determine whether rhC1-INH administered early during hospital admission for COVID-19 provides additional benefit compared to SOC alone with regards to the clinical course of patients by limiting the local and systemic inflammatory response, and to describe its safety profile in this population.

Primary Objective

The primary objective of the study is to determine if adding 4 days of treatment with rhC1-INH to SOC treatment in adult participants admitted with non-critically ill COVID-19 infection will affect disease severity including progression to severe disease requiring mechanical ventilation within 7 days after enrollment as assessed by the WHO Ordinal Scale for Clinical Improvement.

Secondary Objectives

To evaluate the effect of rhC1-INH treatment in addition to SOC treatment compared to only SOC treatment on disease progression as measured by

Time to clinical improvement (time from randomization to an improvement of two points on the seven-category WHO ordinal scale or live discharge from hospital, whichever came first) within 14 days after enrollment.

Proportion of participants alive and not having required invasive or non-invasive ventilation at 14 days after enrollment.

Proportion of subjects with ARDS (defined by Berlin severity criteria) within 14 days after enrollment.

Safety Objectives

The study aims to assess the safety of rhC1-INH treatment in patients admitted with COVID-19 infection and receiving SOC treatment including overall incidence of adverse and serious adverse events and their relationship to the study treatment during a four-week follow-up.

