14.6.1 Adverse events

Adverse events will be coded according to MedDRA. The assessment of Safety will be based mainly on the frequency of AEs that are treatment emergent (TEAEs). Formal statistical tests will not be conducted for differences in safety parameters between treatment groups.

The incidence of all treatment-emergent AEs will be tabulated after grouping by system organ class and preferred term. For each preferred term and summarized over each system organ class overall, the table will present the absolute number and proportion (%) of patients in each treatment group in whom the event occurred. The incidence of all suspected-IMP-related AEs will be tabulated similarly. The incidence of all treatment-emergent AEs will also be tabulated by severity categories.

Safety will also be summarized with respect to vital signs as mean levels by visit and change from baseline. Abnormal observations on physical examinations will be listed.

Summary statistics for the absolute vital sign value and the changes from baseline will be presented using n, mean, standard deviation, median, minimum, and maximum.

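### The safety tables leave out serious adverse events, a stated objective, and give no patient-level count of allergic or thrombo-embolic events and no summary around the 4-day treatment

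*SAP*

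**What the plan says.** SAP 14.6 and 14.6.1 and Protocol 11.4.5 plan three AE layouts:

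- All TEAEs: "The incidence of all treatment-emergent AEs will be tabulated after grouping by system organ class and preferred term", with a patient count and percentage per treatment group for each preferred term and each organ class.
- Drug-related AEs: "The incidence of all suspected-IMP-related AEs will be tabulated similarly".
- Severity: "The incidence of all treatment-emergent AEs will also be tabulated by severity categories".

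There are also vital-sign summaries and a listing of abnormal physical findings. No formal safety tests are planned.

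The safety objective in SAP 4 is wider, "including overall incidence of adverse and serious adverse events and their relationship to the study treatment during a four-week follow-up". Protocol 4.4 states the same objective with a 3-month follow-up. SAP 5.3 also uses 3 months, so the SAP disagrees with itself on the period.

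The protocol gives two kinds of event special attention. Section 3.7 names allergy to residual rabbit material as the one relevant clinical risk known. Section 10.1.4 attaches an individual case review to a "treatment-emergent anaphylactic/anaphylactoid reaction or thrombotic/thrombo-embolic event".

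The Safety Population (SAP 14.2, Protocol 11.4.1) consists of patients given at least one dose of rhC1INH, and it is used for all safety analyses.

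**The concern.** A report that follows the plan to the letter need not state how many patients in each arm had a serious adverse event, although that is part of the objective. Nor need it state how many had an allergic or anaphylactic reaction, or a thrombo-embolic event. Finally, it would not separate events near the 4-day exposure from those collected over the following weeks or months, in patients for whom Protocol 10.1 expects frequent complications of COVID-19.

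**Working it through.** The documents give no safety rate, safety power or safety sample size, so there is no figure of the plan to reproduce. The check is mainly a comparison of texts.

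**1. Requirement against output.**

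| Item | Where it is raised | Planned table |
|---|---|---|
| AE incidence | Protocol 4.4, SAP 4 | Yes, by organ class and preferred term |
| AE relatedness | Protocol 4.4, SAP 4 | Yes, same layout |
| AE severity | Protocol 10.1.1 | Yes |
| SAE incidence and relatedness | Protocol 4.4, SAP 4 | None |
| Patients with any allergic/anaphylactic event | Protocol 3.7, 10.1.4 | None |
| Patients with any thrombotic/thrombo-embolic event | Protocol 10.1.4 | None |
| Events around treatment | 4-day exposure, Protocol 8.2.1 | None |

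**2. Can another output stand in for an SAE table?** The severity table cannot, because Protocol 10.1.1 tells investigators to keep seriousness and intensity apart. The related-AE table is a subset and is not by seriousness. The aggregated table in Protocol 10.1.2 belongs to the annual safety update and covers suspected serious reactions, not all SAEs by arm. The DSMB's data (Protocol 1.3) serve monitoring, not the final analysis.

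**3. Can the grouped counts be read off preferred-term rows?** Not in general. Protocol 7.1 names deep vein thrombosis and pulmonary embolism separately, and one patient may have both. For rows with counts a, b, c, the number of patients with at least one event lies between max(a, b, c) and a + b + c. Illustration with assumed rates: 15% of 80 rhC1INH patients is 12 patients. If they fall evenly in three rows, each row shows 4. A reader of those rows knows only that the total is between 4 and 12 patients (5% to 15%).

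**4. How large a part of the AE period is the treatment window?** Dosing is on Days 0-3. Adding 7 days, the onset window used for the product's known events ("that occurred with onset within 7 days of treatment with rhC1INH", Protocol 3.7), gives Days 0-10, or 11 days.

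- 3-month period: 11/98 = 11% (14 weeks, Protocol 6.1) to 11/92 = 12% (3 calendar months).
- Four-week period: 11/28 = 39%, or 11/32 = 34% if four weeks run from the end of the 4 treatment days.

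On either reading, most of the period lies outside the window. Effect of background events, with assumed rates: risks of 10% and 2% have a ratio of 5.0. With an independent background risk b in both arms, each risk becomes 1 - (1 - p)(1 - b). For b = 5% this gives 14.5% and 6.9%, ratio 2.1. For b = 20% it gives 28.0% and 21.6%, ratio 1.3. The risk difference moves less, from 8.0 to 7.6 and 6.4 percentage points.

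**5. Would added tables have a control column?** Not as defined. SOC-only patients never receive rhC1INH, so they fall outside the Safety Population, although Protocol 11.4.5 and SAP 14.6.1 promise figures for each treatment group. Protocol 10.1.1 starts treatment emergence at first treatment, which has no counterpart in the SOC arm.

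**6. What the added tables could show.** With 80 and 40 patients, two-sided 5%, and the pooled standard error under the null:

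- 15% vs 5%: (0.10 - 1.96 × 0.0622)/0.0527 = -0.41, power about 34%.
- 10% vs 5%: (0.05 - 1.96 × 0.0535)/0.0481 = -1.14, power about 13%.
- No events in 80: upper bound 1 - 0.05^(1/80) = 3.7% (one-sided 95%) or 1 - 0.025^(1/80) = 4.5% (two-sided 95%).

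**The case against.** The case against the grouped and early-onset tables is substantial.

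- **AEs are not tabulated only by organ class and preferred term.** A reader might infer this, but relatedness and severity are also tabulated, and each organ class has a patient-level total. The relatedness table removes some COVID-19 events, although causality is judged open-label and the rows are still preferred terms.
- **Deaths are not missing.** Grade 5 in the severity scale is fatal, and all-cause mortality within four weeks is a listed outcome.
- **The documents do not support a sizeable allergy rate.** A reader might suppose, say, 5% lost across several rows. Protocol 8.6 calls anaphylaxis exceptionally rare, seen in one patient with rabbit allergy, and such patients are excluded. If that patient was among the 268 exposed (assumption), the rate is 1/268 = 0.4%, or 0.3 expected in 80. How terms would spread over the coding dictionary is not in the documents either.
- **Thrombo-embolism is not an established harm of the drug here.** Protocol 3.5 reports no evidence of it. Section 10.1.4 is a rule for individual patients, not a reporting category.
- **Comparability with the product's 7-day profile is not an objective.** The planned comparison is with SOC, and a matched window would not make the populations alike. Days 0-10 also cover much of the acute illness.

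All of this stands, and it limits the second and third parts to improvements in reporting. It does not touch the missing SAE table. One may expect the report to show SAEs anyway, but neither document commits to it.

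**Conclusion.** The concern holds in a limited form. SAE incidence and relatedness is a stated objective with no planned analysis in either document. This rests on the text alone and needs no assumed rate. The missing grouped counts and treatment-window summary are not errors, but they are worth adding because the protocol itself singles out these events and the exposure is short. Their size cannot be derived from the documents. The rates used above are assumptions that show direction only, apart from the window's share of follow-up (11-12% of 3 months, 34-39% of four weeks), which depends on which stated period applies and on the 7-day margin.

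It would be wrong to conclude that the plan hides a known frequent harm, or that grouping would give the trial power to detect harms. It gives readable counts with intervals. The primary efficacy analysis is unaffected.

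**What to change.** Add to SAP 14.6.1, by arm, with counts, percentages and confidence intervals:

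1. SAEs by organ class and preferred term, and by relatedness.
2. Number and percentage of patients with at least one allergic/anaphylactic event, and with at least one thrombotic/thrombo-embolic event, with day of onset. Use a list of grouped terms fixed before AE data are seen by arm.
3. The organ class/preferred term table repeated for early onset (for example Days 0-10), beside the full-period table.

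Two changes are needed for these to compare arms. Amend the Safety Population in SAP 14.2 and Protocol 11.4.1 (and the synopsis) to include SOC patients, analysed as treated, with Day 0 as the start of treatment emergence for controls. Reconcile the four-week AE period in SAP 4 with the 3 months in Protocol 4.4 and SAP 5.3.

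The cost is wording plus three descriptive tables. Seriousness, relatedness and onset are already recorded for each AE (Protocol 9.1.4.1), and MedDRA coding is already planned. The downside is that grouped terms will pick up some COVID-19 events, so the by-arm contrast matters more than the rate in one arm.

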14.7 Multi-site study

Individual site results will be presented by means of descriptive statistical methods for the demographical and primary efficacy data.

	Trial Substance:	Ruconest®	Study No.: C1 6201 PROTECT-COVID-19-US
	Short Title:	Ruconest®: Prevention of severe SARS-CoV-2 infection in hospitalized patients with COVID-19	Sponsor: Pharming Technologies B. V.

14.8 Multiplicity

Pocock's group sequential approach is used and the significance levels in the interim analysis are adjusted for the primary variable accordingly ($\alpha_p = 0.0221$).

14.9 Handling of missing data and drop-outs

Withdrawn/discontinued participants will not be replaced. Missing data for the primary variable will be imputed by means of the Last-observation-carried forward (LOCF) method, as sensitivity analyses some alternative imputation methods like imputation of the mean and multiple imputation will be additionally performed.

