6. STUDY DESIGN

6.1 General Study Design and Justification of Design

This is an exploratory, randomized, parallel-group, open-label, multi-center, phase 2 clinical study in patients with confirmed COVID-19 infection and admitted to the hospital for treatment of SARS-CoV-2 infection to estimate the effect size of rhC1INH treatment compared to SOC on the proportion of patients surviving without requiring mechanical ventilation.

The study will recruit approximately 120 patients (80 patients in the intervention and 40 in the control arm) from approximately five to ten sites in the United States. Sites will be selected on the basis of estimated numbers of cases, the availability of a committed principal site Investigator and research team, and the capacity to collect samples as per protocol.

Participants will be randomly assigned in a 2:1 ratio to rhC1INH treatment in addition to standard of care (SOC) or SOC stratified by the site. Screening, informed consent and randomization will happen as early as possible after admission to the hospital, usually within 48 hours after admission. Participants will receive intravenous rhC1INH in addition to standard of care (SOC) or SOC during an admission period starting on the day after informed consent (=day 0). Both groups will continue to receive SOC treatment for COVID-19 infection. Blood samples will be collected before and during the 4-day period of treatment. Follow-up will include the period until discharge and a weekly telemedicine interview or telephone call for 3 months post treatment to assess potential adverse events and outcomes.

Duration of participant's participation will be approximately 14 weeks (+/- 5 days). Screening phase duration is up to 48 hours; intervention period is 14 days (including a treatment phase of 4 days) and follow-up period of 3 months starting post-treatment on Day 0. After discharge, follow-up information is obtained on a weekly basis until 3 months post-treatment. When no response is received within 5 weeks following discharge the participant may be considered as lost to follow-up.

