⁴IMP will be administered every 12 hours (+/-15 minutes) for 4 days. A total of 8 doses will be administered. Trial medication will be stopped in participants in whom PCR results are not consistent with confirmed COVID-19 and in patients that are discharged or transferred to another facility.

⁵A Serum hCG pregnancy test will be performed in women who may become pregnant, are sexually active, and do not use adequate contraceptive measures.

⁶Collection of samples will be once daily before 1st administration of study medication (day 0 through day 3) and once daily until hospital discharge.

⁷The worst value recorded on a given day will be documented.

⁸Oxygenation levels will be measured for patients on oxygen while hospitalized.

⁹3-months follow-up period begins post-treatment (Day 0). Assessments will be done daily until discharge and weekly via telemedicine interview or telephone call post-discharge.

¹⁰Monitoring of prolonged QT intervals in severely-ill subjects receiving multiple drugs.

Assessments of outcomes

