9.1.4 Assessment of Safety Outcomes

9.1.4.1 Adverse events

Participants will be followed for adverse events and outcomes for 3 months post treatment (Day 0). Assessments will be done daily while in the hospital and via a weekly follow-up telemedicine interview or telephone call after discharge.

Adverse events and clinical course including death within 4 weeks will be assessed by a weekly telemedicine or structured telephone interview for 3 months post-treatment. If necessary, medical charts will be reviewed, discharge summaries will be reviewed, or the patients' general practitioner will be contacted regarding specific follow-up information.

Every effort will be made to contact the trial subject and obtain complete data for follow-up. Conditions that started before signing informed consent will be recorded as medical history. Conditions that started or deteriorated after signing informed consent will be documented as AE. Definition of AE and SAE will be found in Section 10.

All AEs will be assessed and documented by the Investigators according to seriousness, intensity, causal relationship with study treatment, action taken with study treatment (e.g. withdrawal), specific treatment for AE and outcome. In addition, time of onset and AE duration will be recorded. Procedures are defined in Section 10. AEs will be recorded on the respective CRF pages. Participants will be asked about any new events/complaints during the hospitalization and up to 3 months post treatment. In addition, participants are asked to report any new events including hospital admission to the study team.

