- Routine laboratory tests will be performed daily during admission according to standard procedures, and should include a set of hematology, coagulation and biochemistry parameters. Additionally, blood (7ml) for analysis of ferritin, IL-6, D-Dimer, C1INH concentration will be collected at the same time point.
- Monitoring of prolonged QT intervals in severely-ill subjects receiving multiple drugs.
- Measurement of oxygenation levels.
- Monitor your heart rhythms in severely-ill subjects receiving multiple drugs
- Assessment of AEs and concomitant medications

Visit 5, Intervention period (Day 3-13 during hospital admission)

- Assessment of physical examination
- Completion of treatment with rhC1INH (150 U/ml) at a 50 U/kg dose (max dose of 4200 U) every 12 hours (8 doses in total) in the active treatment group as per treatment schedule. The time of dosing and the dose will be recorded. (Treatment to be administer at Visit 5 on Day 3 ONLY)
- Assessment of vital signs including respiratory rate.
- Assessment of WHO ordinal scale and need for oxygen supplementation.
- Documentation of ICU admission and/or non-invasive or invasive ventilation
- Routine laboratory tests will be performed daily during admission according to standard procedures, and should include a set of hematology, coagulation and biochemistry parameters. Additionally, blood (7ml) for analysis of ferritin, IL-6, D-Dimer, C1INH concentration will be collected at the same time point. and collection of blood for the analysis of complement proteins (C3 & C4).
- Virological assessment (SARS-CoV-2 PCR in respiratory specimen) should be performed on day 4-7 (according to local standard).
- Monitoring of prolonged QT intervals in severely-ill subjects receiving multiple drugs.

- Measurement of oxygenation levels.
- Monitor your heart rhythms in severely-ill subjects receiving multiple drugs
- Assessment of AEs and concomitant medications

Visit 6, Follow-up (Day 14 (+/-2 days) or at discharge)

- Physical examination including body weight.
- Assessment of vital signs including respiratory rate.
- Assessment of WHO ordinal scale and need for oxygen supplementation
- Documentation of ICU admission and/or non-invasive or invasive ventilation

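### The primary LOCF rule makes no exception for live discharge, so a patient who goes home before Day 7 and has no recorded Day-7 score can be analysed at an inpatient score

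*SAP*

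**What the plan says.** The primary endpoint is the WHO score on Day 7: 1-2 for outpatients, 3-6 for inpatients, 7 for death (Protocol 5.1). Protocol 9.1.1 and 9.1.2 ask for the scale on every day after enrolment, and the worst score of the calendar day counts.

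The schedule is narrower. The visit that covers Day 7 is "Visit 5, Intervention period (Day 3-13 during hospital admission". Visit 6, which includes a WHO score, takes place on Day 14 or at discharge. Footnote 9 to the flow chart states: "Assessments will be done daily until discharge and weekly via telemedicine interview or telephone call post-discharge". The weekly call (Visit 7) includes the WHO scale. Protocol 6.1 gives the start as a "follow-up period of 3 months starting post-treatment on Day 0", and footnote 9 and Protocol 9.1.4.1 likewise join post-treatment to Day 0. Yet Day 0 is the first dosing day, and the last doses fall at Visit 5: "Treatment to be administer at Visit 5 on Day 3 ONLY". SAP 3 and the SAP 5.8 schedule place Visit 7 around week 4 and 3 months. SAP 15 refers back to the protocol visits and gives no Day-7 window.

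For a missing Day-7 score, SAP 14.9 says: "Missing data for the primary variable will be imputed by means of the Last-observation-carried forward (LOCF) method". SAP 14.2 and Protocol 11.4.1 and 11.5 say the same. Mean imputation and multiple imputation are named as sensitivity analyses. None of these sections mentions discharge. Live discharge counts as success only in the time-to-improvement endpoint (Protocol 5.2, SAP 5.1.2).

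**The concern.** Entry requires only an expected stay of four calendar days (Protocol 7.1), so discharge on Days 4 to 6 is foreseeable. If such a patient has no Day-7 score and no contact between discharge and Day 7, the last observation is from the hospital. It is 3 or higher under the worst-of-day rule, unless the site records the state after discharge at Visit 6; no section says which governs. A patient who is at home is then tied with one still in hospital without oxygen, or ranked worse if the carried score is 4.

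The error falls on the patients who did well. If rhC1INH shortens the stay, more rhC1INH than SOC scores are raised, and the estimated benefit shrinks. The interim looks use the same endpoint, can change the sample size, and may lead the data monitoring board to recommend stopping for insufficient results. The sample-size text (Protocol 11.2, SAP 6) relies on hospitalisation to secure the Day-7 score, but that describes patients at entry, not on Day 7.

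**Working it through.** **When the first weekly call falls.** Counted from Day 0: Day 7. Counted from the last dosing day: 3 + 7 = Day 10. Counted from discharge on Day 4, 5 or 6: Day 11, 12 or 13. Only the Day-0 count places a call on Day 7 itself.

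**The plan's own sample size.** With a difference of 1 point, SD 1.5, two-sided 0.05 and power 0.80, n per arm = 2 x (1.960 + 0.842)^2 / (1/1.5)^2 = 35.3, so 36. The t-based version gives 36.3, so 37, against 38 stated. For the total, 92 x 1.125 (2:1 allocation) x 1.165 (three-look Pocock inflation) = 120.6, against 120. The plan's figure reproduces and does not depend on the LOCF rule.

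**Effect on the mean difference.** Let m be the share of discharged patients without a Day-7 score, pT and pC the shares discharged on rhC1INH and SOC, c the carried score, and oT and oC the true mean outpatient scores. Then

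loss = m x [pT x (c - oT) - pC x (c - oC)].

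With 10% of SOC discharged (29.5% on rhC1INH) and c = 3:
- m = 25%: 0.25 x [0.295 x 1.447 - 0.100 x 1.385] = 0.072, so 1.0 becomes 0.93.
- m = 50%: 0.50 x [0.295 x 1.447 - 0.100 x 1.385] = 0.144, so 1.0 becomes 0.86.

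**Effect on power (simulation, 40,000 trials per cell).** From the plan: a 1.0-point difference, 80 versus 40 patients, SAP looks at 40, 80 and 120, a rank test stratified by baseline score, inverse-normal combination (equal weights), and a cut-off of 2.289 (two-sided 0.0221) at each look.

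Assumed, because the documents do not give them:
- 70% of patients have baseline score 4 and 30% score 3.
- SOC Day-7 probabilities for scores 1-7 at baseline 4 in four scenarios: .03 .05 .19 .36 .15 .14 .08; .065 .10 .20 .345 .11 .11 .07; .10 .155 .21 .295 .10 .09 .05; .18 .27 .18 .20 .07 .07 .03. At baseline 3 the cumulative odds of a lower score are doubled.
- A common odds ratio for rhC1INH that gives 1.0 point (3.84, 3.43, 3.43, 4.00).
- Equal missing shares in both arms, and every affected score carried as 3.

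| Discharged by Day 7, SOC / rhC1INH | 10% / 30% | 20% / 46% | 30% / 59% | 50% / 80% |
|---|---|---|---|---|
| Power, all Day-7 scores known | 0.94 | 0.90 | 0.90 | 0.95 |
| 10% of discharged missing | 0.94 | 0.89 | 0.88 | 0.91 |
| 25% missing | 0.93 | 0.87 | 0.85 | 0.83 |
| 50% missing | 0.93 | 0.85 | 0.80 | 0.72 |
| Mean difference, 25% missing | 0.93 | 0.90 | 0.88 | 0.85 |
| Mean difference, 50% missing | 0.86 | 0.80 | 0.76 | 0.70 |

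Power values vary by about 0.01 between repeat runs. At 25% missing, the number of mis-scored patients is 0.25 x (80 x pT + 40 x pC), or about 7, 11, 15 and 21 of 120. With no true effect and equal missing shares, the two-sided error is 0.045-0.051.

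**Sensitivity to the assumptions.** A different SOC distribution (20/22/20/18/9/7/4% for scores 1-7; unstratified test) gives power of 0.89 with all scores known. At 25% missing it falls to 0.79 if scores are carried as 3 and to 0.65 if carried as 4. The size therefore depends heavily on inputs that the documents do not supply.

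**The case against.** The protocol does ask for the Day-7 score. Sections 9.1.1 and 9.1.2 require daily scoring without limiting it to inpatients, and the scale has outpatient levels. Day 0 is the named clock, and weekly calls from Day 0 reach Day 7. A call on Days 10 to 13, or the chart, discharge-summary and general-practitioner follow-up allowed at Visit 7, can still establish where the patient was on Day 7; discharge dates and deaths are recorded (Protocol 9.1.3). The blind review (SAP 12) can also deal with irregular data before lock.

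Most of this stands. It rules out the stronger inference that outpatients go unscored by design, or that early discharges will certainly be mis-scored. Nor does Protocol 6.1 permit a Day-7 score to be skipped where it says "When no response is received within 5 weeks following discharge the participant may be considered as lost to follow-up": that sentence defines loss to follow-up.

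What remains is a conflict between daily and weekly scoring, and a stated LOCF rule that gives the wrong score whenever the contact fails. Record review applies only where necessary and carries no scoring instruction. The blind review comes after the interim looks.

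The size is also fairly contested. All discharge and missing shares are assumed, and in the table power stays above the planned 0.80 at 10% and 25% missing. The simulation covers baseline scores 3 and 4 only, although patients on high-flow oxygen (score 5) are not excluded.

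**Conclusion.** The point holds as a conditional one. A patient discharged home before Day 7 without a recorded Day-7 score can be analysed at 3 or higher instead of 1-2, because the primary rule has no provision for live discharge. If rhC1INH speeds discharge and contact is missed equally in both arms, the bias is toward no effect. Under the listed assumptions, with scores carried as 3, the loss in power is at most about 0.04 at 10% missing, about 0.01-0.12 at 25% and about 0.01-0.24 at 50%. It is zero if every early discharge is contacted. The documents do not allow the size to be derived.

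A reader might infer that the false-positive rate is inflated, or that power collapses. The first needs contact rates that differ by arm. With no true effect, and 25% missing on rhC1INH against 50% on SOC, the chance of a false result favouring rhC1INH is 0.027-0.089 instead of 0.025. The second needs an extreme case: all discharged patients missing and 30% of them carried as 4, which gives power of 0.33-0.85. The open-label design makes unequal contact possible, but nothing in the documents supports either pattern. Both are illustrations only.

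The point should be fixed, because it concerns the primary endpoint and the remedy is cheap.

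**What to change.** 1. Reconcile Protocol 9.1.1-9.1.2 with the flow chart, Protocol 9.2.1 and SAP 3 and 5.8. State that weekly contacts count from Day 0, and schedule a Day-7 WHO-scale call for patients already discharged, with its window in SAP 15. Allow Day-7 status to be established later from a call, chart or discharge summary. State which score governs on the day of discharge.
2. In SAP 14.2 and 14.9 and Protocol 11.4.1 and 11.5, add a step before LOCF. A patient discharged home alive, with no known readmission or death by Day 7, is scored as outpatient at one prespecified value, for example 2, the less favourable outpatient score. Death by Day 7 is scored 7. Transfer to another facility is not discharge home. LOCF is limited to unknown status. The same rule applies at the interim looks.
3. Keep at least one sensitivity analysis that does not assume uncontacted discharged patients stayed at home, such as multiple imputation allowing readmission, or a worse score. Report the Day-7 contact rate by arm.
4. Reword the sentence in Protocol 11.2 and SAP 6 that relies on hospitalisation to secure the Day-7 score.

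In the four scenarios, scoring uncontacted patients as 2 gives power of 0.94, 0.90, 0.89 and 0.92 at 25% missing, and 0.94, 0.89, 0.88 and 0.89 at 50%. The cost is one call per early discharge and some wording, since calls that include the scale already exist. The price is a small assumption about uncontacted patients, which item 3 tests.
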